## 11.9. Appendix 9: Abbreviations & Trade Marks

### 11.9.1. Abbreviations

Abbreviation	Description
AE	Adverse Event
AESI	Adverse Events of Special Interest
ATRA	All Trans-Retinoic Acid
A&R	Analysis and Reporting
CI	Confidence Interval
CPMS	Clinical Pharmacology Modelling & Simulation
CRF	Case Report Form
CS	Clinical Statistics
CSR	Clinical Study Report
CTCAE	Common Terminology Criteria for Adverse Events
CTR	Clinical Trial Register
DBF	Database Freeze
DBR	Database Release
DOB	Date of Birth
DLT	Dose Limiting Toxicity
DP	Decimal Places
eCRF	Electronic Case Record Form
FDA	Food and Drug Administration
FDAAA	Food and Drug Administration Clinical Results Disclosure Requirements
GSK	GlaxoSmithKline
IA	Interim Analysis
ICH	International Conference on Harmonization
IDSL	Integrated Data Standards Library
IP	Investigational Product
MOCA	Montreal Cognitive Assessment
MTD	Maximum Tolerated Dose
NCI	National Cancer Institute
PCI	Potential Clinical Importance
PDMP	Protocol Deviation Management Plan
PK	Pharmacokinetic
PD	Pharmacodynamic
PP	Per Protocol
QC	Quality Control
QTcF	Frederica's QT Interval Corrected for Heart Rate
QTcB	Bazett's QT Interval Corrected for Heart Rate
RAP	Reporting & Analysis Plan
RP2D	Recommended Phase 2 Dose
SAC	Statistical Analysis Complete
SOP	Standard Operation Procedure
TA	Therapeutic Area
TFL	Tables, Figures & Listings

**11.9.2. Trademarks**

Trademarks of the GlaxoSmithKline Group of Companies
NONE

Trademarks not owned by the GlaxoSmithKline Group of Companies
SAS
WinNonlin

## 11.10. Appendix 10: List of Data Displays

### 11.10.1. Data Display Numbering

The following numbering will be applied for RAP generated displays:

Section	Tables	Figures
Study Population	1.1 to 1.15	N. A
Efficacy	2.1	N. A
Safety	3.1 to 3.20	N. A
Pharmacokinetic	4.1 to 4.6	N. A
Section	Listings	
ICH Listings	1 to 34	
Other Listings	35 to 48	

### 11.10.2. Mock Example Shell Referencing

Non IDSL specifications will be referenced as indicated and if required example mock-up displays provided in [Appendix 11](#): Example Mock Shells for Data Displays.

Section	Figure	Table	Listing
Study Population	POP_Fn	POP_Tn	POP_Ln
Efficacy	EFF_Fn	EFF_Tn	EFF_Ln
Safety	SAFE_Fn	SAFE_Tn	SAFE_Ln
Pharmacokinetic	PK_Fn	PK_Tn	PK_Ln
Population Pharmacokinetic (PopPK)	POPPK_Fn	POPPK_Tn	POPPK_Ln
Pharmacodynamic and / or Biomarker	PD_Fn	PD_Tn	PD_Ln
Pharmacokinetic / Pharmacodynamic	PKPD_Fn	PKPD_Tn	PK/PD_Ln

**NOTES:**

- Non-Standard displays are indicated in the 'IDSL / Example Shell' or 'Programming Notes' column as '[Non-Standard] + Reference.'

### 11.10.3. Deliverables

Delivery	Description
SAC	Final Statistical Analysis Complete

## 11.10.4. Study Population Tables

Study Population Tables					
No.	Population	IDSL / Example Shell	Title	Programming Notes	Deliverable
Subject Disposition					
1.1.	All Treated Subjects	ES1	Summary of Participant Disposition for the Participant Conclusion Record	ICH E3, FDAAA, EudraCT	SAC
1.2.	All Treated Subjects	SD1	Summary of Treatment Status and Reasons for Discontinuation of Study Treatment		SAC
1.3.	Enrolled	NS1	Summary of Number of Participant by Country and Site ID	EudraCT/Clinical Operations	SAC
Demographic and Baseline Characteristics					
1.4.	All Treated Subjects	DM1	Summary of Demographic Characteristics	ICH E3, FDAAA, EudraCT	SAC
1.5.	Enrolled	DM11	Summary of Age Ranges	EudraCT	SAC
1.6.	All Treated Subjects	DM5	Summary of Race and Racial Combinations	ICH E3, FDA, FDAAA, EudraCT	SAC
Medical History and Concomitant Medications					
1.7.	All Treated Subjects	MH1	Summary of Current/Past Medical Conditions		SAC
1.8.	All Treated Subjects	CM8	Summary of Concomitant Medications	Include both prior and concomitant medications	SAC
Exposure and Treatment Compliance					
1.9.	All Treated Subjects	POP_T1	Summary of Exposure to GSK2879552	Include 2mg QD/ATRA 45mg/m2/day	SAC

Study Population Tables					
No.	Population	IDSL / Example Shell	Title	Programming Notes	Deliverable
1.10.	All Treated Subjects	ODMOD1	Summary of Dose Reductions to GSK2879552		SAC
1.11.	All Treated Subjects	ODMOD8	Summary of Dose Escalations to GSK2879552		SAC
1.12.	All Treated Subjects	ODMOD2	Summary of Dose Interruptions to GSK2879552		SAC
Prior Anti-Cancer Therapy and Surgical Procedures					
1.13.	All Treated Subjects	AC1	Summary of Prior Anti-Cancer Therapy		SAC
1.14.	All Treated Subjects	AC3	Summary of Number of Prior Anti-Cancer Therapy Regimens		SAC
1.15.	All Treated Subjects	OSP1	Summary of Cancer Related Surgical Procedures		SAC

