A graphical presentation of the prior is displayed in the [Figure 2](#). In the figure, the x-axis is natural log (dose/reference dose), where the reference dose is set to 5 mg. Doses are the projected doses. Actual doses used during the conduct of the trial may vary.

Figure 2 Prior Distribution For The Probability of DLT Given Dose**4.2.2. GSK2879552 and ATRA combination**

In Cohort 1, three subjects will receive GSK2879552 2 mg once daily dose with ATRA 45 mg/m²/day as two divided doses. After all three subjects complete the first 4 weeks of treatment, the safety data will be reviewed for DLT. Available PK and PD data will be also reviewed prior to a dose escalation decision and starting Cohort 2. Each cohort will enroll 3 or more subjects to obtain sufficient data. If any subject becomes unevaluable for reasons other than toxicity, a replacement subject will be enrolled. In addition, subjects who fail to take at least 75% of their scheduled doses of each drug in the first 4 weeks for reasons other than toxicity will be replaced. Starting with Cohort1, the dose escalation will use the N-CRM with prior DLT information of GSK2879552 and ATRA monotherapies and follow the same rule with regards to the number of subjects, maximum dose increment, and the completion of dose escalation as described in Section 4.2.1. The details of priors used in N-CRM model is described in Section 13.2.

Starting at dose level 1, the following GSK2879552 dose levels are planned for evaluation in combination with ATRA..

Dose level	GSK2879552	ATRA
1	2 mg/day	45 mg/m ² /day
2	4 mg/day	45 mg/m ² /day
3	8 mg/day	45 mg/m ² /day
4	12 mg/day	45 mg/m ² /day
5	20 mg/day	45 mg/m ² /day

A reduced dose of GSK2879552 or ATRA may be considered if the combination is not well tolerated at dose level 1. The initial dose level reductions allow for either drug to be reduced. Subsequent dose levels are based on the totality of data and upon discussion with the investigators.

Dose level	GSK2879552 ATRA fixed at 45mg/m ²
-1	1 mg/day
-2	0.5 mg/day

Dose level	GSK2879552
	ATRA <30mg/m ²
1a	2 mg/day
-1a	1 mg/day
-2a	0.5 mg/day

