4.8.2. Dose Adjustment for Non-Hematologic Toxicity

See [Table 2](#) Dose Adjustment Guideline for drug related non-hematologic toxicities based on worst grade.

Table 2 Dose Adjustment Guideline for Drug Related Non-Hematologic Toxicity

Worst Grade	Dose Adjustment
G1	No change in dose
G2 [†]	Continue dosing with no change OR Consider holding for up to 2 weeks for toxicity to resolve to baseline or ≤ Grade 1, then continue at the same dose OR dose reduce by at least 25% if the toxicity is considered a DLT.
G3 and 4 [†]	Hold for up to 2 weeks for toxicity to resolve to baseline or ≤ Grade 1, then dose reduce by at least 25%. If no recovery to ≤Grade 1* or baseline after 14 days, patient should be withdrawn.

*Note: Exceptions to ≤ drug-related Grade 1 requirement may be made for rash, alopecia, quickly reversible (<72 hours) laboratory abnormality (example: electrolyte changes).

[†]In combination cohort, consider holding ATRA dosing first for skin related toxicity (dryness, rash), nausea, vomiting, pain, headache, and mucositis. With fever, consider holding LSD1 first to allow neutrophil count to recover.

If the non-hematologic toxicity or event resolves to baseline or ≤ Grade 1 within 14 days of stopping therapy, treatment with GSK2879552 and/or ATRA may be restarted with at least **25%** dose reduction. For a non-DLT, the treatment with GSK2879552 could restart at a full dose, if deemed appropriate.

If the non-hematologic toxicity does not resolve to ≤ Grade 1 or baseline within 14 days, the subject should be withdrawn from the treatment permanently (Section 6.3). However, if the investigator and GSK Medical Monitor agree that further treatment will benefit the subject, treatment can restart with at least **25%** dose reduction once the toxicity resolves to ≤ Grade 1 or baseline.

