4.8.4.2. Liver Function Test Elevation

If ALT \geq 5 X ULN, ATRA dose should be held while GSK2879552 dosing continues

- If resolved in 14 days, ATRA dose should resume at full dose
- If not resolved in 14 days, GSK2879552 dose should be also held.
 - If resolved in another 14 days, resume GSK2879552 at a reduced dose by minimum 25% and ATRA at full dose
 - If not resolved in another 14 days, withdraw the subject from the study.

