### 2.2. Study Objective(s) and Endpoint(s)

Part 1 Objectives	Part 1 Endpoints
Primary Objectives	Primary Endpoints

 
To determine the safety, tolerability, MTD and/or RP2D and regimen of GSK2879552, alone or in combination with ATRA, given orally in adult subjects with AML.
 
	
 
AEs, SAEs, dose limiting toxicities, dose reductions or delays, withdrawals due to toxicities and changes in safety parameters (e.g., laboratory values, vital signs, electrocardiograms [ECGs], physical examinations).
 

Secondary Objectives	Secondary Endpoints

 
To characterize the PK of GSK2879552, alone or in combination with ATRA, after single and repeat-dose oral administration.
 
	
 
GSK2879552 PK parameters following single-(Day 1) and repeat-dose (Day 15) administration of GSK2879552, including AUC, Cmax, tmax, t1/2 (terminal phase and/or effective half-life), accumulation ratio, and time invariance
 

 
To evaluate clinical response after treatment with GSK2879552, alone or in combination with ATRA.
 
	
 
Objective response rate defined as the percentage of subjects achieving complete remission (CR), partial remission (PR), CRp (as per CR but platelet
 

[figure not shown]
Part 1 Objectives	Part 1 Endpoints
	Count <100 x 10  /L) and morphologic leukemia free state per response criteria (Cheson, 2003).

 
To characterize the PK of ATRA in combination with GSK2879552 after single and repeat-dose oral administration.
 
	
 
ATRA PK parameters following single and repeat-dose administration of ATRA and GSK2879552, including AUC, Cmax, tmax, t1/2 (terminal phase).
 

Exploratory Objectives	Exploratory Endpoints

 
To explore markers of differentiation (including morphology) in response to GSK2879552, alone or in combination with ATRA.
 
	
 
Change from baseline expression in cell surface markers in AML cells derived from bone marrow and/or peripheral blood.
 

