### 11.6.2. Study Population

Demography
Age

 
• Age will be calculated based on the Screening visit date
 
• Birth date will be imputed as follows:             
 
Any subject with a missing day will have this imputed as day ‘15’.
 
Any subject with a missing date and month will have this imputed as ‘30JUN’.
 
 
 

Body Mass Index

 
• Calculated as weight (kg) / [height (m)]
 

Extent of Exposure

 
• Number of days of exposure to study drug will be calculated based on the formula:             
 
Duration of Exposure in Days = Treatment Stop Date – (Treatment Start Date) + 1
 
 
 
• Participants who were randomized but did not report a treatment start date will be categorised as having zero days of exposure.
 
• The cumulative dose will be based on the formula:             
 
Cumulative Dose = Sum of (Number of Days x Total Daily Dose)
 
 
 
• If there are any treatment breaks during the study, exposure data will be adjusted accordingly.
 
• Note: GSK2879552 exposure data will only be used for the above calculation.
 

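### SAP Tables 1.9, 1.10 and 1.12 cover GSK2879552 only, so a combination subject whose only dose change is to ATRA would be summarised as having none

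*SAP*

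**What the plan says.** The Part 1 primary objective in SAP 2.2 is "To determine the safety, tolerability, MTD and/or RP2D and regimen of GSK2879552, alone or in combination with ATRA". Its endpoint is "AEs, SAEs, dose limiting toxicities, dose reductions or delays, withdrawals due to toxicities and changes in safety parameters". Protocol Section 5 uses the term study treatment for either drug or for both together.

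SAP 6.6 says that every dose reduction, escalation and interruption will be both summarised and listed. It names no drug in that sentence.

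The display list in SAP 11.10.4 is narrower. Table 1.9 is "Summary of Exposure to GSK2879552", with a programming note to include the 2 mg plus ATRA group. Table 1.10 (reductions) and Table 1.11 (escalations) are titled for the same drug, and Table 1.12 is "Summary of Dose Interruptions to GSK2879552". No table title covers ATRA exposure or ATRA dose changes. Under Extent of Exposure, SAP 11.6.2 adds: "Note: GSK2879552 exposure data will only be used for the above calculation".

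The protocol allows the two drugs to be modified separately. The footnote to Table 2 in Protocol 4.8.2 reads: "In combination cohort, consider holding ATRA dosing first for skin related toxicity (dryness, rash), nausea, vomiting, pain, headache, and mucositis". For ALT at or above 5 x ULN, Protocol 4.8.4.2 says "ATRA dose should be held while GSK2879552 dosing continues". Protocol 4.8.4.3 has ATRA held for moderate to severe pseudotumor cerebri.

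**The concern.** The combination group sits inside these tables but is described by only one of its two drugs. The protocol itself creates the situation in which that matters: a toxicity leads to ATRA being stopped for a time while GSK2879552 carries on. Such a subject has had a toxicity-driven dose change, which is a named component of the primary endpoint, yet adds nothing to the summary of that component.

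The combination column would then stand beside the monotherapy columns on a definition that fits monotherapy completely and the combination only in part. A reader working from the summary tables would have no sign of this, because SAP 6.6 says everything is summarised and SAP Table 1 records only the loss of ATRA pharmacokinetics.

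**Working it through.** No sample size, power or error rate is involved, and the plan gives no figure to reproduce. The check sets the provisions side by side and then sizes one missed subject.

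**1. Scope promised against scope delivered**

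| Item | Source | Drugs covered |
|---|---|---|
| Primary endpoint component: reductions or delays | SAP 2.2 | GSK2879552 alone or with ATRA |
| Undertaking to summarise and list all modifications | SAP 6.6 | No drug named |
| Exposure, reduction and interruption tables (1.9, 1.10, 1.12) | SAP 11.10.4 | GSK2879552 |
| Derivation of exposure duration and cumulative dose | SAP 11.6.2 | GSK2879552 |
| Listings of exposure, reductions, interruptions, escalations (11-14) | SAP 11.10.8 | No drug named |
| Declared changes from the protocol | SAP Table 1 | ATRA pharmacokinetics only |

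The body text and the display list therefore disagree, and the disagreement is not declared.

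**2. One subject followed through the tables.** A combination subject reaches ALT at or above 5 x ULN. Under Protocol 4.8.4.2 ATRA is held, GSK2879552 continues, the elevation resolves within 14 days and ATRA resumes. Table 1.12 counts no interruption, Table 1.10 counts no reduction, and the GSK2879552 exposure in Table 1.9 is unchanged. The hold appears in no summary of dose modification.

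**3. Size.** Let *n* be the number of combination subjects, *g* the number with any GSK2879552 modification, and *k* the number whose only modification is to ATRA.

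- Proportion with a modification of either drug: (*g* + *k*)/*n*
- Proportion shown by tables limited to GSK2879552: *g*/*n*
- Shortfall: *k*/*n*

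Protocol 4.2.2 plans three subjects in the first combination cohort and three or more in each cohort. SAP 5.1 shows one combination dose level. The final number is not given, so *n* = 3 to 6 is an assumption.

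- *n* = 3: *k* = 0, 1, 2 or 3 gives a shortfall of 0, 33, 67 or 100 percentage points.
- *n* = 6: each ATRA-only subject gives 1/6 = 17 percentage points.

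The documents do not give *k*.

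**4. Table 1.11.** The planned escalation levels in Protocol 4.2.2 keep ATRA at 45 mg/m²/day throughout, so leaving ATRA out of the escalation table loses nothing of substance.

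**The case against.** The strongest reply is that the information is probably not lost. Listings 11-14 are not limited to a drug, and the note to Listing 3 asks for the investigational product as a column, so the SAP does separate the drugs at subject level. With one combination dose level and perhaps three to six subjects, a listing can be read line by line. The 11.6.2 note governs only exposure duration and cumulative dose. The study closed early, the report is abbreviated and the analysis is descriptive. All of this stands, and it limits the consequence. It does not remove the gap, because SAP 6.6 promises summaries as well as listings, and the templates that would show whether the listings identify the drug are not in the documents.

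A reader might also infer more than the documents support:

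- **That ATRA is always the first drug held.** The wording is to consider it for the toxicities in the Table 2 footnote, and for fever that footnote points to the other drug. Only the ALT and pseudotumor cerebri provisions say it should be held.
- **That ATRA's reported event rates indicate how many holds would be missed.** The figures in Protocol 1.3.6.1 (for example headache 86%, nausea/vomiting 57%) come from the prescribing information and are given without grade, whereas the footnote attaches to the Grade 2 and Grade 3-4 rows. For raised liver tests (50% to 60%), the same section says most resolve without ATRA being interrupted or after treatment ends. These are not hold rates.
- **That the combination would look better tolerated overall.** The adverse event tables (3.1-3.6) and the hepatobiliary table (3.11) record the toxicities whichever drug was held.
- **That nobody could tell whether DLT-free subjects received enough ATRA.** Protocol 4.2.2 replaces "subjects who fail to take at least 75% of their scheduled doses of each drug in the first 4 weeks" for reasons other than toxicity, and the dose-escalation committee reviews dosing logs under Protocol 4.2.1. That check does not depend on Table 1.9.

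**Conclusion.** The point holds as a reporting gap on a named component of the primary endpoint, and it should be corrected. The summary tables for exposure, reductions and interruptions are narrower than both the endpoint and SAP 6.6, and SAP Table 1 does not say so.

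The effect is conditional. The combination's modification rate could be understated; whether it is depends on ATRA-only changes having occurred. The per-subject sizes above rest on the assumed cohort of three to six and on the table titles meaning what they say. The gap is in the summaries of dose modification, and the documents do not show that the events would be absent from the report as a whole. The point concerns reporting only and takes no position on which drug should be held.

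**What to change.** For the 2 mg QD/ATRA column:

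- Table 1.9: add ATRA rows, at least for duration and average daily dose. These match the rows already in the POP_T1 shell. A percent-of-planned-dose row is not needed; it would require a body surface area derivation that SAP 11.6.2 does not contain.
- Tables 1.10 and 1.12: add ATRA rows and an either-drug row, and retitle accordingly.
- SAP 11.6.2: limit the note to the GSK2879552 rows.
- Listings 11-14: add a programming note that the drug be identified, as is already done for Listing 3.

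Table 1.11 needs no change. A flag for subjects taking less than 75% of either drug in the first 28 days is optional. If the sponsor prefers to keep the tables to GSK2879552, SAP 6.6 should be narrowed and the omission declared and justified in SAP Table 1.

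The cost is a few table rows. Protocol 5.4 already has compliance, capsule counts and the dates of delays and reductions recorded, and Protocol Section 5 brings ATRA within the study treatment to which this applies.

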11.10.5. Efficacy Tables

Efficacy: Tables					
No.	Population	IDSL / Example Shell	Title	Programming Notes	Deliverable
Clinical Response					
2.1.	All Treated Subjects	Re1a	Summary of Investigator-Assessed Best Response (Without Confirmation)	
 
1. Investigator Assessed Responses would be reported. No confirmation on responses are required.
 
2. Include the response categories collected in eCRF. i.e. 1. Complete remission (CR) 2. As per CR but PLT < 100 x10^9/L (CRp) 3. Morphologic leukaemia-free state (MLFS) 4. Partial remission (PR) 5. Stable disease 6. Progressive Disease or Relapse of Disease 7. Not evaluable
 
3. Include just the first two segments of the template. i.e. Best Response and Response rate.
 
4. Response rate = CR+CRp+MLFS+PR
 
5. P-value for response rate would not be reported.
 
	SAC

## 11.10.6. Safety Tables

Safety: Tables					
No.	Population	IDSL / Example Shell	Title	Programming Notes	Deliverable
Adverse Events (AEs)					
3.1.	All Treated Subjects	OAE7	Summary of All Adverse Events by Maximum Grade by System Organ Class and Preferred Term		SAC
3.2.	All Treated Subjects	AE3	Summary of All Adverse Events by System Organ Class and Preferred Term		SAC
3.3.	All Treated Subjects	AE13	Overview of Adverse Events		SAC
3.4.	All Treated Subjects	IDSL AE's of Special Interest – EXAMPLE METABOLIC 14.1	Summary of All Adverse Events of Special Interest		SAC
3.5.	All Treated Subjects	AE15	Summary of Common ( $\geq 5\%$ ) Non-serious Adverse Events by System Organ Class and Preferred Term (Number of Participant and Occurrences)	FDAAA, EudraCT	SAC
Serious and Other Significant Adverse Events					
3.6.	All Treated Subjects	AE16	Summary of Serious Adverse Events by System Organ Class and Preferred Term (Number of Participants and Occurrences)	FDAAA, EudraCT	SAC

Safety: Tables					
No.	Population	IDSL / Example Shell	Title	Programming Notes	Deliverable
Please Laboratory: Chemistry					
3.7.	All Treated Subjects	OLB9C	Summary of Clinical Chemistry Toxicity Grade Change from Baseline Grade	For gradable Clinical chemistry tests. By dose, and overall. Include Worst-case.	SAC
3.8.	All Treated Subjects	OLB11C	Summary of Clinical Chemistry Laboratory Changes from Baseline with Respect to the Normal Range	For non-gradable lab tests. By dose, and overall.	SAC
Laboratory: Hematology					
3.9.	All Treated Subjects	OLB9C	Summary of Haematology Toxicity Grade Change from Baseline Grade	For gradable Haematology tests. By dose, and overall. Include Worst-case.	SAC
3.10.	All Treated Subjects	OLB11C	Summary of Clinical Hematology Laboratory Changes from Baseline with Respect to the Normal Range	For non-gradable lab tests. By dose, and overall.	SAC
Laboratory: Hepatobiliary (Liver)					
3.11.	All Treated Subjects	LIVER10	Summary of Hepatobiliary Laboratory Abnormalities		SAC
ECG					
3.12.	All Treated Subjects	EG1	Summary of ECG Findings		SAC
3.13.	All Treated Subjects	EG10	Summary of Maximum QTc Values Post-Baseline Relative to Baseline by Category		SAC
3.14.	All Treated Subjects	EG11	Summary of Maximum Increase in QTc Values Post-Baseline Relative to Baseline by Category		SAC
3.15.	All Treated Subjects	SAF_T1	Summary of Maximum QTc Grades Post-Baseline Relative to Baseline		SAC

Safety: Tables					
No.	Population	IDSL / Example Shell	Title	Programming Notes	Deliverable
3.16.	All Treated Subjects	SAF_T1	Summary of Maximum Increase in QTc Grades Post-Baseline Relative to Baseline		SAC
Vital Signs					
3.17.	All Treated Subjects	OVT1B	Summary of Changes in Heart Rate from Baseline		SAC
3.18.	All Treated Subjects	OVT2B	Summary of Increases in Blood Pressure from Baseline		SAC
3.19.	All Treated Subjects	OVT1B	Summary of Changes in Temperature from Baseline	The following categories need to be included: Decrease to <=35 Change to normal or no change Increase to >=38	SAC
ECOG					
3.20.	All Treated Subjects	PS4A	Summary of Change in ECOG 'Performance Status' from Baseline		SAC

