13.8. Key Elements of Analysis Plan

Data will be listed and summarized according to the GSK reporting standards, where applicable. Data will be listed and summarized mostly by doses. Separate analyses will be provided for Part I and in Part II where applicable. In some instances, analysis may also be generated based on the dose of GSK2879552. Data from Part I and Part II may be combined for some analyses at the end of the trial, for subjects treated at the same dose level. Complete details will be documented in the Reporting and Analysis Plan (RAP). Any deviations from, or additions to, the original analysis plan described in this protocol will be documented in the RAP and final study report.

As it is anticipated that accrual will be spread thinly across centers and summaries of data by center would be unlikely to be information, data from all participating centers will be pooled prior to analysis.

All data up to the time of study completion/withdrawal from study will be included in the analysis, regardless of duration of treatment.

As the duration of treatment for a given subject will depend on efficacy and tolerability, the duration of follow-up will vary between subjects. Consequently there will be no imputation for missing data.

Demographic and baseline characteristics will be summarized.

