13.8.2. Safety Analyses

The All Treated Subjects Population will be used for the analysis of safety data. All serially collected safety endpoints (e.g. laboratory tests, vital signs, electrocardiogram [ECGs]) will be summarized according to the scheduled, nominal visit at which they were collected and across all on-treatment time points using a “worst-case” analysis. Complete details of the safety analyses will be provided in the Reporting and Analysis Plan (RAP).

Safety endpoints are described in Section 2. Complete details of the safety analyses will be provided in the RAP.

A listing by subject including treatment administered, and compliance, will be generated with dates and times of treatment administered. The number of subjects exposed to study drug will be tabulated for Part 1 (for each dose cohort) and Part 2.

All relevant safety data will be listed and summarized according to IDSL standards. The reporting and analysis plan will list the IDSL templates for the displays. Adverse events will be coded and grouped by system organ class (SOC) and preferred (coded) term (PT) using the Medical Dictionary for Regulatory Activities (MedDRA) system for adverse event coding. AEs will be graded according to the National Cancer Institute Common Terminology Criteria for Adverse Events (NCI CTCAE) Version 4.03. Adverse events will be summarized by maximum toxicity grade for each initial dose level. All AEs will be listed. A summary of the number and percent of subjects reporting each AE at least once will be produced for all AEs, for drug-related AEs and for SAEs for Part 1 (for each dose cohort) and Part 2. A listing of those AEs identified as dose-limiting toxicities will also be produced for each dose cohort for Part 1. A listing showing the relationship of AE

verbatim text to group terms and body systems will also be produced. A listing of withdrawals due to AEs will be provided. Deaths and SAEs will be listed should they occur.

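### Three adverse-event displays that the protocol specifies for Part 1 (drug-related AEs by term, DLTs by dose cohort, withdrawals due to AEs) are missing from the SAP display list, and their omission is not declared

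*SAP*

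**What the plan says.** Protocol 13.8.2 sets out the AE displays. The number and percent of subjects reporting each AE "will be produced for all AEs, for drug-related AEs and for SAEs for Part 1 (for each dose cohort) and Part 2". It continues: "A listing of those AEs identified as dose-limiting toxicities will also be produced for each dose cohort for Part 1". For stopping treatment it says: "A listing of withdrawals due to AEs will be provided".

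Protocol 13.8 sets the rule for changes: "Any deviations from, or additions to, the original analysis plan described in this protocol will be documented in the RAP and final study report".

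SAP 2.2 repeats the Part 1 primary endpoint unchanged: "AEs, SAEs, dose limiting toxicities, dose reductions or delays, withdrawals due to toxicities and changes in safety parameters".

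SAP 11.10.6 then plans six AE tables:
- 3.1, all AEs by maximum grade
- 3.2, "Summary of All Adverse Events by System Organ Class and Preferred Term"
- 3.3, "Overview of Adverse Events"
- 3.4, AEs of special interest
- 3.5, common non-serious AEs
- 3.6, SAEs by term

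SAP section 7 presents safety summaries by dose level. SAP Table 1 declares three changes from the protocol: no Part 2 analysis, an abbreviated instead of a full report because the study was terminated, and no ATRA pharmacokinetic analysis.

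**The concern.** A SAP may cut displays after early termination, but the protocol requires each departure to be written down. Here three displays specified in one protocol paragraph disappear without being named. If the SAP is followed as written, they will not be produced, and a reader of the report will not know that they had been planned.

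The three matter for different reasons.

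- **DLTs** are a named component of the primary endpoint. They also define the MTD (protocol 4.2.6).
- **Relatedness** enters the escalation rules in protocol 4.2.1. Subject to stated exceptions, a related non-hematologic AE of Grade 2 or higher raises the minimum cohort size from 1 to 2 subjects and lowers the maximum dose increment from 100% to 50%. A by-term table of related events by dose would summarise the events behind those decisions.
- **Withdrawals due to toxicity** are also part of the primary endpoint. A reason category shows that a subject stopped because of an AE, but not necessarily which AE.

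**Working it through.** No formula applies, and the plan gives no figure to reproduce. The check sets each AE display in protocol 13.8.2 against the SAP.

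**Size of the display list.** SAP 11.10.1 numbers Tables 1.1–1.15, 2.1, 3.1–3.20 and 4.1–4.6, so 15 + 1 + 20 + 6 = 42 tables, and Listings 1–48. SAP 11.10.4 to 11.10.9 fill these ranges without gaps.

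**AE displays, protocol against SAP.**

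| Protocol 13.8.2 | SAP display | Named as dropped in SAP Table 1? |
|---|---|---|
| AEs by maximum grade, by initial dose level | Table 3.1 | – |
| Listing of all AEs | Listing 15 | – |
| Subjects with each AE, all AEs | Table 3.2 | – |
| Subjects with each AE, drug-related | none | no |
| Subjects with each AE, SAEs | Table 3.6 | – |
| DLT listing by dose cohort | none | no |
| Verbatim text against coded terms | Listing 17 | – |
| Listing of withdrawals due to AEs | none (reasons only: Table 1.2, Listings 2 and 3) | no |
| Deaths and SAEs listed | Listings 28, 29 and 44 | – |

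Six of the nine are planned and three are not. Of the three by-term summaries, two are planned and the drug-related one is missing. Of the two special listings, neither is planned.

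**SAP text.** SAP 7.1 does not mention drug-related AEs. It refers to other significant AEs and points to the display list for detail. The blocks headed for serious and other significant AEs hold only SAE displays (Table 3.6, Listings 28 and 29).

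**Primary-endpoint components against planned displays.**
- AEs: Tables 3.1–3.5
- SAEs: Table 3.6
- Dose reductions or delays: Tables 1.10 and 1.12
- Safety parameters: Tables 3.7–3.19, with no physical-examination display
- Withdrawals due to toxicities: partly covered, by reason, in Table 1.2 and Listings 2 and 3
- DLTs: no display

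Of six components, four have a planned display, one is partly covered and one has none.

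**Declaration.** SAP Table 1 has three rows, and none names an AE display. The ATRA row shows the level of detail that the sponsor applied elsewhere: it states the dropped analysis and the reason for dropping it. The abbreviated-report row gives a reason for a reduced report but does not say which displays go.

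**The case against.** The strongest reply is that the study was stopped early, that the SAP declares an abbreviated report for that reason, and that what remains is ample. The endpoint lists AEs without asking for relatedness. Tables 3.1, 3.2, 3.4 and 3.6 give AEs by term, grade or category of interest, by dose level. Subjects who stopped for an AE can be found: protocol 6.3 requires AE to be recorded as the primary reason when a subject voluntarily stops for toxicity, and those subjects can be cross-read with the full AE listing. Most of this stands, and it limits the point to three specific displays.

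A reader might go further and infer that the Part 1 safety objective cannot be read from the planned tables. The documents do not support that. Four of the six endpoint components have displays and a fifth is partly covered.

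A reader might also argue from protocol 1.3.5 that all-causality rates cannot differ by dose, because 11 of 11 subjects had an AE and 11 of 11 had an SAE at the 20-NOV-2015 cut. That saturates only the any-event row. Rates by term and grade can still vary: apart from febrile neutropenia, no SAE occurred in more than one subject. With 1, 2, 7 and 1 subjects at the four doses (1 + 2 + 7 + 1 = 11), that cut could not show a dose pattern either way. Nor can the all-causality tables be dismissed as pure disease background. Protocol 8.1, 8.3 and 8.4 keep expected disease signs, disease-associated findings and natural-course events out of AE or SAE reporting unless they are worse than expected.

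One uncertainty remains. The templates for the overview table (AE13) and the AE listings (OAE04) are not reproduced, so they may carry relatedness counts or flags. This cannot be confirmed, and an overview count or a subject-level flag would still not be a by-term table by dose.

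**Conclusion.** The omission is real but limited. Three protocol-specified Part 1 safety displays are neither planned in the SAP nor named among its declared changes: the drug-related AE summary by term and dose cohort, the DLT listing by dose cohort, and the listing of withdrawals due to AEs. This conflicts with the documentation rule in protocol 13.8, and the general declaration of an abbreviated report does not meet that rule for specific displays.

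The DLT listing is the most consequential of the three, because DLTs are a primary-endpoint component with no other planned display. The drug-related table is a loss of interpretability, not of an endpoint. The withdrawal gap is partial: reasons are planned, but nothing in the documents shows that Table 1.2 or Listings 2 and 3 name the event.

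This should be corrected in the SAP. It does not undermine the design, and the safety objective remains largely answerable. The conclusion rests on display titles and SAP text, since the contents of the standard templates are not given.

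**What to change.** Add three items to SAP 11.10, with matching sentences in SAP 7.1:

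1. Drug-related AEs by system organ class and preferred term, and by maximum grade, by dose level. These are Tables 3.2 and 3.1 filtered on relatedness. The by-term table is what the protocol specifies; the by-grade version goes slightly beyond it.
2. A listing of AEs leading to permanent discontinuation of study treatment or to withdrawal, naming the event, grade and relatedness.
3. A listing of AEs that were DLTs, by Part 1 dose cohort.

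If any of these is to be dropped because the report is abbreviated, name it in SAP Table 1 with the reason, as was done for the ATRA pharmacokinetics.

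The cost is two filtered repeats of existing shells and two listings from data already collected, or a few lines in SAP Table 1.
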